**Part A:**

Approximately 70 subjects who are currently not being treated for their CHB infection will be randomized in a 3:1:3 ratio to receive one of the following treatments:

- Treatment Arm 1: JNJ-56136379 (N=30) (open-label)

After full recruitment, this treatment arm was discontinued early per Protocol Amendment 4. All subjects were to stop further dosing with JNJ-56136379 75 mg, start treatment with NA, and enter the post-treatment follow-up phase (Schedule 1).

- Treatment Arm 2: Placebo + NA (ETV or TDF) (N=10)
- Treatment Arm 3: JNJ-56136379 + NA (ETV or TDF) (N=30)

At the same time, approximately 40 subjects who are virologically suppressed by current NA treatment will be randomized in a 1:3 ratio to receive one of the following treatments:

- Treatment Arm 4: Placebo + NA (ETV or TDF) (N=10)
- Treatment Arm 5: JNJ-56136379 + NA (ETV or TDF) (N=30)

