## **6.2. Futility Rule**

Per Protocol Amendment 4, as a precautionary measure to safeguard the subjects, a futility rule for the JNJ-56136379 250 mg monotherapy arm (Treatment Arm 6) has been installed: if  $\geq 1$  subject in the 250 mg monotherapy arm experiences virological breakthrough during the first 24 weeks of treatment, NA treatment will be added to JNJ-56136379 treatment as soon as possible for all remaining subjects. These subjects will continue the visit schedule as planned. Subjects with virological breakthrough will discontinue JNJ-56136379 treatment (see Section 10.2) and should start NA treatment.

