### **2.1. Analysis Sets**

*Screened Population or all subjects* consists of all subjects, i.e. screening failures and (not) randomized subjects.

---

*Safety population* consists of all subjects who received at least one dose of the study agent and all safety endpoints will be analyzed by the treatment arm as treated.

*Intent-to-Treat Population (ITT)*: all subjects who are randomized and received at least one dose of any study agent. If a subject receives a study agent other than their randomly assigned study agent, subjects will be shown in the treatment arm as randomized.

The analysis population will be indicated in the title of each table and listing.

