**Table 1: Construction of phases**

Analysis phase	Analysis Period	Start date	End date
Screening (phase 1)		The date of signing the informed consent	1 day before the first study agent intake
Treatment (phase 2)	Initial Treatment	Date of first study agent intake	- If not included in the treatment extension°: Date of last study agent intake + 5 days*

Analysis phase	Analysis Period	Start date	End date
	(period 1)		- If included in the treatment extension o : Date of Week 24 study agent intake+5 days #
	Treatment Extension (period 2)	End of the initial treatment period + 1 day	Date of last study agent intake + 5 days*
Follow-up (phase 3)		End of the treatment phase +1 day	Trial termination date (date of last contact) or cut-off date for an interim analysis, whichever comes first

o depending on the answer in the FA dataset: FAOBJ = " WILL THE SUBJECT CONTINUE TREATMENT IN TREATMENT EXTENSION PHASE?" and whether actually treatment was extended in the EX dataset.

\* or study termination date (date of last contact) or cut-off date for an interim analysis, whichever comes first.

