### 5.2.1 Parameter Definitions

The following parameters will be derived as follows:

*Viral breakthrough during 24 weeks of treatment (all subjects), during 48 weeks of treatment (subject with treatment extension) and during NA follow up for all subject who switch to NA-treatment during follow-up:*

HBV virological breakthrough is defined as having a confirmed on-treatment HBV DNA increase by  $>1$  log10 from nadir level (lowest level reached during 24/48 weeks treatment) or a confirmed on-treatment HBV DNA level  $>200$  IU/mL in subjects who had HBV DNA level below the lower limit of quantification (LLOQ) of the HBV DNA assay.

The proportion of subjects with a viral breakthrough is defined as follows:

---

- 0 (No) = subject has not had a viral breakthrough (see definition above) up to the considered time point
- 1 (Yes) = subject has a viral breakthrough at the considered time point or has had a viral breakthrough before (regardless of the HBV DNA result at the considered time point)
- 2 (No: ongoing): subject has not had a viral breakthrough (see definition above) up to the last time point but is still ongoing (only for interim analysis)

Confirmed means that the criterion should be fulfilled at 2 or more consecutive time points or at the last observed time point on-treatment. On-treatment means in the treatment phase, except for the baseline record.

The proportion of subjects with a viral breakthrough during initial 24- or 48-weeks treatment but still on NA Treatment (Yes / No)

Note: For Viral breakthrough during NA follow up, only subject on NA treatment will be include in the denominator.

*Viral relapse* is defined in the follow-up phase as follows:

- 1 (Yes) = viral relapse: confirmed  $\geq 2000$  IU/mL quantifiable.
- 0 (No) = no viral relapse: at least one post-treatment measurement available and not a viral relapse
- 2 (Not applicable) = no post-treatment HBV DNA measurements available
- 3 (No: ongoing) = no viral relapse: at least one post-treatment measurement available and not a viral relapse but still ongoing (only for interim analysis)

Confirmed means that the criterion should be fulfilled at 2 or more consecutive time points or at the last observed time point.

Note: viral relapse will only be assessed for those subjects who at the actual end of treatment have HBV DNA  $< 20$  IU/ml detectable/ undetectable.

*Biochemical relapse* is defined in the follow-up phase as follows:

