**Table 5: Time to event definitions and censored data**

Variables	Definition	Censored data
HBsAg Response	Time to a HBsAg level of $<1000$ IU/mL	Subjects who did not achieve “HBsAg $<xxx$ IU/mL” will be censored at the last HBsAg assessment
	Time to a HBsAg level $<100$ IU/mL	
	Time to a HBsAg level $<10$ IU/mL	
	Time to a HBsAg level $<0.05$ IU/mL	
HBsAg Reduction	Time to a HBsAg reduction of $> 0.3 \log_{10}$ IU/mL	Subjects who did not reduce HBsAg by “ $>xxx \log_{10}$ IU/mL” from baseline will be censored at the last HBsAg assessment
	Time to a HBsAg reduction of $> 0.5 \log_{10}$ IU/mL	
	Time to a HBsAg reduction of $> 1 \log_{10}$ IU/mL	
	Time to a HBsAg reduction of $> 2 \log_{10}$ IU/mL	
	Time to a HBsAg reduction of $> 3 \log_{10}$ IU/mL	
HBsAg Seroclearance (in all subjects)	Time to HBsAg seroclearance as defined in section 5.3.1	Subjects who did not achieve HBsAg seroclearance will be censored at the last HBsAg assessment
HBeAg Seroclearance (in HBeAg-positive subjects only)	Time to HBeAg seroclearance as defined in section 5.3.1	Subjects who did not achieve HBeAg seroclearance will be censored at the last HBeAg assessment
HBeAg Reduction	Time to a HBeAg reduction of $> 0.5 \log_{10}$ IU/mL from baseline	Subjects who did not achieve “HBeAg $<xxx$ IU/mL” from baseline will be censored at the last HBeAg assessment
	Time to a HBeAg reduction of $> 1 \log_{10}$ IU/mL from baseline	
	Time to a HBeAg reduction of $> 2 \log_{10}$ IU/mL from baseline	
HBV virological breakthrough	Time to HBV virological breakthrough as defined in section 5.3.1	Subjects who did not achieve HBV virological breakthrough will be censored at the last HBV DNA assessment during the defined time frame

HBV DNA Response	Time to a HBV DNA level <1 log10 IU/mL	Subjects who did not achieve “HBV DNA <xx log 10” will be censored at the last HBV DNA assessment
	Time to a HBV DNA level <2 log10 IU/mL	
	Time to a HBV DNA level <3 log10 IU/mL	
	Time to a HBV DNA level <100 IU/mL	Subjects who did not achieve “HBV DNA<xxxx IU/mL” will be censored at the last HBV DNA assessment
	Time to a HBV DNA level <1000 IU/mL	
	Time to a HBV DNA level <2000 IU/mL	
	Time to a HBV DNA level <20000 IU/mL	
	Time to HBV DNA < LLQ for target detected and not detected	Subjects who did not achieve HBV DNA<LLQ for both target will be censored at the last HBV DNA assessment

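### If the 250 mg futility rule fires, time on JNJ-56136379 + NA counts as event-free monotherapy time and the Arm 6 breakthrough rate is diluted; the Arm 1 crude rate is not a 24-week risk

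*SAP*

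**What the plan says.** The breakthrough proportion (SAP 5.3, Parameter Definitions) has a Yes code, a No code and an interim-only code for subjects still ongoing. The No code reads: "0 (No) = subject has not had a viral breakthrough (see definition above) up to the considered time point". No code exists for a subject whose monotherapy was ended by the sponsor or who received NA by rule.

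Four other SAP provisions settle who is counted and for how long:
- The efficacy set is ITT (SAP 2.1): "all subjects who are randomized and received at least one dose of any study agent".
- SAP 5.3: "On-treatment means in the treatment phase, except for the baseline record". For subjects not in the extension, the treatment phase ends at "Date of last study agent intake + 5 days" (SAP Table 1). SAP section 2 limits study agent to JNJ-56136379 and placebo, so starting NA does not end the phase.
- On confirmation, SAP 5.3 says: "Confirmed means that the criterion should be fulfilled at 2 or more consecutive time points or at the last observed time point on-treatment".
- For time to breakthrough, SAP Table 5 says: "Subjects who did not achieve HBV virological breakthrough will be censored at the last HBV DNA assessment during the defined time frame".

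The protocol sets out two ways in which monotherapy ends before Week 24 without a breakthrough. For Arm 1 (Protocol 3.1, Part A): "After full recruitment, this treatment arm was discontinued early per Protocol Amendment 4". For Arm 6, after at least one breakthrough in the first 24 weeks (Protocol 6.2): "NA treatment will be added to JNJ-56136379 treatment as soon as possible for all remaining subjects". Those Arm 6 subjects keep their visit schedule. The SAP does not mention the Arm 6 rule.

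**The concern.** A reader will take the tabulated proportion for a monotherapy arm as the risk of breakthrough over 24 weeks of monotherapy. It has that meaning only if subjects without an event were observed on monotherapy for 24 weeks.

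In Arm 6, the event being counted is also the event that ends monotherapy for everyone else. Subjects protected by NA from then on remain in the denominator as non-events. In Arm 1, the closure ends observation early for an unknown number of subjects, and they too become non-events.

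Breakthrough is a secondary endpoint, and it is the finding that closed Arm 1 and led to the Arm 6 rule. If the two crude proportions are set side by side, 250 mg can look better than 75 mg even when the underlying risks are equal.

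**Working it through.** **Starting figures.** The documents plan no breakthrough rate, so there is no design figure to reproduce. The only stated figure is the Arm 1 count at 6 February 2019 (Protocol 1.3.4): 5 confirmed of 28, with 2 more over the threshold but unconfirmed because treatment changed. Planned size is 30 in Arm 1, and Part B has the same format, so Arm 6 is taken as 30.

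**Does the Arm 6 rule matter in practice?** It fires if at least one of 30 subjects breaks through: P = 1 - (1 - p)^30.
- p = 5%: 78.5%
- p = 10%: 95.8%
- p = 17.9% (5/28): 99.7%
- p = 25% (7/28): above 99.9%

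Without the rule, expected events are 30p: 3.0, 5.4 and 7.5 at 10%, 17.9% and 25%.

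**What is reported once it fires?** The documents give no entry dates or NA lag, so these are assumptions. In simulation A, onset is uniform over Weeks 8-24, entry is spread over 13-39 weeks, NA is added 2-4 weeks after the first event, and there is no breakthrough after NA. The crude proportion is events seen divided by 30.

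| True 24-week risk | Crude proportion | Ratio, true to reported |
|---|---|---|
| 17.9% | 4.0-6.4% | 17.9/6.4 = 2.8 to 17.9/4.0 = 4.5 |
| 25% | 4.3-7.4% | 25/7.4 = 3.4 to 25/4.3 = 5.8 |

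More than one event is seen in 19-67% of these runs. The two true risks give nearly the same reported range.

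Simulation B uses wider assumptions: entry over 0-52 weeks, onset from Week 4, confirmation lag 2-4 weeks, NA lag 1-4 weeks.

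| True risk | Mean confirmed events | Crude proportion | More than one event |
|---|---|---|---|
| 10% | 1.0-1.7 | 3.3-5.5% | 5-49% |
| 17.9% | 1.1-2.3 | 3.6-7.7% | 8-74% |
| 25% | 1.1-2.9 | 3.7-9.6% | 10-86% |

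The high ends combine simultaneous entry with a 4-week NA lag. At a true 10% the dilution is smaller: 10/5.5 = 1.8 to 10/3.3 = 3.0.

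**Does censoring at NA start help?** Under the assumptions of simulation A, the product-limit estimate censored there averages 14-24% at a true 17.9% and 17-28% at a true 25%. Its 5th-95th percentile range at 17.9% runs from about 4% up to 33-56%, depending on entry spread.

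**Arm 1.** The closure pulls the count in two directions.
- Crude, protocol count: 5/28 = 17.9% (exact 95% CI 6.1-36.9%).
- Crude, if the last-on-treatment-value rule scores both unconfirmed subjects Yes: 7/28 = 25.0% (10.7-44.9%).
- Allowing for k event-free subjects stopped before Week 24, the actuarial form events/(28 - k/2) gives the range below. The documents do not give k.

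| k | 5 events | 7 events |
|---|---|---|
| 0 | 17.9% | 25.0% |
| 10 | 5/23 = 21.7% | 7/23 = 30.4% |
| 21 | 5/17.5 = 28.6% | 7/17.5 = 40.0% |

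**An asymmetry between the arms.** The closure ends the Arm 1 treatment phase, so a single high value can be the last on-treatment value and count as confirmed. An Arm 6 subject given NA stays in the treatment phase, so a high value just before NA is followed by further on-treatment values and is not counted in that way.

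**The case against.** Three stronger readings are tempting, and the documents do not support them.

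- A reader might infer that Arm 6 is capped at one event by design. It is not. The effect exists only if the rule triggers, and no Arm 6 breakthrough had occurred when Amendment 4 was written. NA is added as soon as possible, not at once, and breakthroughs before NA starts still count. The limit is soft.
- A reader might infer that every subject taken off by the closure is scored 'No' and that Arm 1 is therefore understated. The last-on-treatment-value rule may score the two unconfirmed subjects 'Yes', and the number stopped before Week 24 is not given. The direction cannot be stated.
- A reader might infer that nothing in the SAP allows for early stopping. Table 5 censors, and because the Arm 1 treatment phase ends 5 days after the last dose, it censors Arm 1 at about the closure. What remains is that the SAP names no estimator or output for this variable, and that for Arm 6 it does not censor at NA start.

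It is also fair to say that the stakes are limited. The study has no formal hypothesis testing, and 75 mg versus 250 mg monotherapy is not a listed main comparison. Dose-response is assessed only on NA background. Disposition, exposure, dosing listings and NA rescue tables would let a careful reader see the truncation. That makes the problem visible but does not correct the tabulated rate, for which SAP 5.3 allows differences and confidence intervals between groups.

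**Conclusion.** The point stands in two parts of different strength.

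For Arm 6, if the rule triggers, both the 24-week proportion and the Table 5 variable treat time on JNJ-56136379 + NA as event-free monotherapy time. A true 17.9% would be reported as about 4-6% and a true 25% as about 4-7%, usually on one to three events. This rests on 30 subjects, the assumed onset, entry spread and NA lag, and no breakthrough after NA. Slower NA start or simultaneous entry narrows the gap, and the lower the true risk, the smaller the dilution.

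For Arm 1, the crude proportion cannot be read as a 24-week risk. Early-stopped subjects push it down and single-value confirmation may push it up; which prevails is unknown.

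This should be corrected in the SAP. It does not affect the primary endpoint.

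**What to change.** In SAP 5.3 and Table 5, keep the crude proportion and add the following for Arms 1 and 6:
- cumulative incidence of breakthrough on monotherapy to Week 24, censored at the earlier of last JNJ-56136379 monotherapy dose and first NA dose, with the estimator named;
- number of events, subject-weeks on monotherapy, and number of subjects truncated before Week 24 without an event;
- Arm 6 breakthroughs after NA addition, shown separately as events on JNJ-56136379 + NA;
- a flag on Arm 1 events that rest on a single last on-treatment value.

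The cost is SAP wording and one derived date. NA administration is already to be listed (SAP 4.6), and trial conduct does not change. The price is precision: the wide Arm 6 range shown in the working means the estimate removes most of the dilution but cannot by itself decide between 75 mg and 250 mg. The report should say so.

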Treatment with JNJ-56136379 may lead to emergence of viral variants with reduced susceptibility or resistance to JNJ-56136379. Based on pre-clinical data, these variants remain susceptible to TDF and ETV but might affect treatment options with CAMs in the future.

As of 6 February 2019, virological breakthrough, as defined by the protocol (ie, confirmed on-treatment HBV DNA increase  $>1 \log_{10}$  from nadir level or confirmed on-treatment HBV DNA level  $>200$  IU/mL in subjects who had HBV DNA level below the LLOQ of the HBV DNA assay), was observed in 5 out of the 28 subjects on JNJ-56136379 75 mg monotherapy. In addition, there were 2 subjects who met the virological breakthrough threshold but, due to the change of treatment, the virological breakthrough could not be confirmed. The virological breakthrough in these subjects is expected to be associated with viral resistance to JNJ-56136379. An HBV DNA decline was observed in these subjects upon initiation of NA treatment confirming pre-clinical data showing that viral variants resistant to JNJ-56136379 remain susceptible to NA treatment.

Given the virological breakthroughs observed in the JNJ-56136379 75 mg monotherapy arm (Treatment Arm 1), this treatment arm was discontinued early per Protocol Amendment 4. All subjects were to stop further dosing with JNJ-56136379 75 mg, start treatment with NA, and enter the post-treatment follow-up phase (Schedule 1).

In addition, per Protocol Amendment 4, the duration of treatment with JNJ-56136379 250 mg monotherapy has been limited to a maximum of 24 weeks (see Section 6.1). As an additional precautionary measure to safeguard the subjects, a stringent futility rule has been implemented in the JNJ-56136379 250 mg monotherapy arm (see Section 6.2).

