*Status changes from baseline at week 24 and at week 48 (only subjects with treatment extension)* for HBsAg, HBeAg, anti-HBs and anti-HBe status. Only the qualitative result will be considered. Use the selected time point for the week 24 or 48 visit as described in 2.3. The following categories were defined. The categories can be extended when missing values are present. A borderline result will be mapped as negative.

- Positive to Positive
- Negative to Negative
- Negative to Positive
- Positive to Negative

Maximum decrease from baseline is defined as the minimum value for change of baseline for the viral activity parameters HBeAg, HBsAg, HBVRNA, HBVDNA and HBcrAg)

*Biochemical response* or alanine aminotransferase (ALT) normalization from baseline per post-baseline time point is defined for subjects with elevated ALT (ALT>ULN) at baseline as:

- 0 (No) = ALT>ULN
- 1 (Yes) = ALT $\leq$ ULN

*On-treatment failure during week 24 period is defined as:*

- Subject who has at week 4 HBVDNA < 1log10 IU/mL decline from baseline and confirmed by retesting at week 8 visit (apply only for the naïve treatment population)
- Or for subject who experienced viral breakthrough as defined above

*On-treatment failure during week 48 period is defined as:*

- Subject whom after completed week 24 treatment and still on JNJ-56136379 experienced viral breakthrough as defined above

---

- Subject who did not meet the treatment extension criteria at week 24 as defined in the protocol (this should be derived using the criteria below)
  - Completed 24 weeks of treatment
  - HBVDNA levels < 200 IU/mL at week 20
  - No safety concerns during the initial 24 weeks of treatment
- Subject who did not meet the week 40/44 treatment completion criteria as defined in the protocol (this should be derived using the criteria below)
  - Completed 48 weeks of treatment
  - At week 40 and confirmed at week 44
    - Normal ALT levels or elevated ALT levels by investigator opinion
    - HBV DNA <LLOQ
    - HBeAg negative
    - HBsAg < 500 IU/mL
    - $\geq 1$  log10 IU/mL decline in HBsAg from baseline

*Post-treatment failure during follow-up with NA treatment is defined as:*

Subject who completed study treatment at week 24 and did not met the treatment extension criteria or subject who did not met treatment completion criteria at week 48 as defined above or subjects who discontinued study treatment earlier and experienced viral breakthrough as defined above (NA treatment)

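### The SAP's breakthrough rule does not work in NA follow-up: read literally it cannot count new NA-phase events, and it permits earlier breakthroughs on JNJ-56136379 to be carried in

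*SAP*

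**What the plan says.** SAP 5.3, Parameter Definitions (printed there as 5.2.1), gives one definition of virological breakthrough: a confirmed on-treatment HBV DNA rise of more than 1 log10 from nadir, or a confirmed on-treatment value above 200 IU/mL in a subject who had been below the LLOQ. It is declared for 24 weeks of treatment, for 48 weeks in subjects with the extension, and "during NA follow up for all subject who switch to NA-treatment during follow-up".

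The terms of that definition are:

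- **Nadir:** "nadir level (lowest level reached during 24/48 weeks treatment". No nadir is given for NA follow-up.
- **On-treatment:** "On-treatment means in the treatment phase, except for the baseline record".
- **Confirmation:** "the criterion should be fulfilled at 2 or more consecutive time points or at the last observed time point on-treatment".
- **Status:** positive if breakthrough occurs at the time point, or if the subject "has had a viral breakthrough before (regardless of the HBV DNA result at the considered time point".
- **Denominator:** "For Viral breakthrough during NA follow up, only subject on NA treatment will be include in the denominator".

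The failure category for follow-up with NA includes "subjects who discontinued study treatment earlier and experienced viral breakthrough as defined above (NA treatment". The Secondary Analysis part of SAP 5.3 has a tabulation bullet that names only the 24- and 48-week treatment windows. Its closing list of categorical endpoints, however, includes breakthrough among those reported in both treatment and follow-up.

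**The concern.** Breakthrough is a secondary endpoint and was the reason Arm 1 was closed. Under Protocol Amendment 4, all Arm 1 subjects were to stop JNJ-56136379, start NA and enter follow-up. Protocol 6.2 has Arm 6 subjects with breakthrough stop JNJ-56136379 and start NA. The NA follow-up rate is therefore computed partly in people whose earlier event occurred on a different drug.

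For that rate to describe NA, the rule needs a window that opens when NA starts, a reference level from the NA period, and a meaning of on-treatment that includes NA follow-up. The SAP supplies none of these. The same section does this for viral relapse, which is tied to the follow-up phase and to subjects with HBV DNA below 20 IU/mL at end of treatment. Without an equivalent for breakthrough, two programmers could produce different tables from the same data, and neither table need measure failure of NA.

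**Working it through.** The documents compute no figure from this rule, so there is nothing to reproduce. The check applies the rule to the protocol's own counts.

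**Inputs**

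- Arm 1 at 6 February 2019: 28 subjects, 5 with confirmed breakthrough, and 2 more who met the threshold without confirmation (Protocol 1.3.4).
- Course afterwards: "An HBV DNA decline was observed in these subjects upon initiation of NA treatment" (same section).
- End of treatment phase: last study agent intake plus 5 days (SAP 2.3, Table 1). Study agent means JNJ-56136379 or placebo, not NA (SAP 2).
- HBV DNA decline on NA by FU Week 4 in these subjects: not given. Assumed range 1.0 to 2.89 log10. The upper end is the 4-week mean fall on 75 mg monotherapy in Protocol 3.1, which the protocol likens to ETV and TDF.

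**Step 1: can a new NA-phase event count?** On-treatment ends with the treatment phase, 5 days after the last JNJ-56136379 or placebo dose. HBV DNA values after that are in the follow-up phase and cannot satisfy the definition. Apart from that 5-day margin, the only route to a positive status in NA follow-up is an earlier breakthrough.

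**Step 2: Arm 1 result under each reading.** Assume that all 28 enter NA follow-up on NA and that HBV DNA only falls there. Intervals are Clopper-Pearson 95%.

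- Flag carried across the switch: 5/28 = 17.9% (6.1 to 36.9).
- Flag carried, and the 2 unconfirmed subjects qualify because their last on-treatment value met the criterion: 7/28 = 25.0% (10.7 to 44.9).
- Flag derived per window, on-treatment read literally: 0/28, but essentially by construction, since a real NA breakthrough would not count either.
- Flag, window and nadir restarted at NA start: 0/28 = 0% (0 to 12.3), and a real NA breakthrough would count.

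**Step 3: effect of the nadir alone.** This requires setting the on-treatment restriction aside. Let R be the log10 height of HBV DNA above the JNJ-phase nadir at the switch, and D the decline on NA by FU Week 4. While HBV DNA is falling, the FU Week 2 value is above the Week 4 value, so both visits exceed the 1 log10 limit only if R − D > 1, that is R > 1 + D.

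- D = 1.0: R > 2.0 log10. D = 2.89: R > 3.89 log10.
- Under the 200 IU/mL criterion, HBV DNA at the switch must exceed 200 × 10^D: 200 × 10^1.0 = 2,000 IU/mL, or 200 × 10^2.89 ≈ 155,000 IU/mL.

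The error can also go the other way. If the NA-phase nadir lies d log10 below the JNJ-phase nadir, a rise of x from the NA nadir is scored as x − d. Events with 1 < x ≤ 1 + d are then missed on the nadir criterion.

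**The case against.** A reader might infer that the SAP scores rescued monotherapy subjects as NA failures. The documents do not support that as a statement of fact. No sentence carries the flag from one window to another, and several point to derivation per window. The three windows are named separately. Breakthrough in the initial treatment among subjects still on NA is its own item. The NA follow-up failure category carries a qualifier in parentheses referring to NA treatment. Time to breakthrough (SAP Table 5) is censored within a defined time frame.

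A reader might also infer that the resistance analyses are mistimed. That is not shown. SAP 7.1 takes the sequence closest to the breakthrough, and a carried flag creates no new event time. It also has separate time points for end of JNJ-56136379 treatment and end of study.

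Further, the planned listings and individual plots would show the HBV DNA decline on NA, the study does no formal hypothesis testing, and the primary endpoint is not involved.

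These points limit the finding but do not remove it. The censoring rule governs non-events and sets no window start, nadir or restart. The NA qualifier follows a reference back to the same definition. Even if every window is derived separately, the on-treatment sentence leaves NA follow-up with a rate that cannot register a new event.

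**Conclusion.** The concern holds in limited form: breakthrough during NA follow-up is declared as an endpoint but is not workably defined. Followed literally, the rule cannot count new NA-phase events and permits earlier breakthroughs on JNJ-56136379 to supply the positives. The possible distortion in Arm 1 is 17.9%, or 25.0% with the unconfirmed cases, against 0%. It depends on the flag being carried, on all 28 subjects being on NA in follow-up, and on HBV DNA only falling there. Derived per window, those 5 subjects are not carried.

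Reuse of the study-treatment nadir is secondary. It mislabels a falling HBV DNA only after a rebound of more than about 2.0 to 3.9 log10, on an assumed NA decline, and it can also hide a true NA breakthrough. Severity is moderate: the effect is confined to secondary and failure tabulations.

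**What to change.** In SAP 5.3, define a separate variable for breakthrough during NA follow-up:

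- the window and the flag start at NA start, with the flag at No;
- on-treatment, for this variable, means on NA in the follow-up phase;
- the nadir and the below-LLOQ condition use HBV DNA on or after NA start;
- subjects with an earlier study-treatment breakthrough stay in the denominator but are positive only for a new event.

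Use this variable in the failure definition for follow-up with NA, and keep study-treatment breakthrough as its own variable. The cost is SAP wording and one derived variable, using NA start dates and HBV DNA results already collected. No clinical rule changes.
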